For patients who require dual chamber pacing, patients will be randomized to His bundle versus left bundle area pacing for active fixation. We will evaluate the acute and follow-up capture threshold of His bundle versus left bundle pacing.

Objectives

Primary Objective

To compare 3 month follow up complete ventricular capture thresholds of His bundle pacing versus left bundle area pacing lead placement. Complete loss of capture will be measured with a width of 1.0 ms and during unipolar or bipolar output, whichever value is lower.

Secondary Objectives

To compare changes in left ventricular performance and mechanical synchrony, selective or non selective-His Pacing, left bundle area pacing, in patients who require ventricular pacing at 3 months.

The endpoints collected will be:

1. Ejection Fraction
2. Stroke volume
3. Mechanical dyssynchrony, characterized by the time to peak systolic velocity of the Left Ventricle (LV) myocardial walls, elicited by tissue Doppler:
 - a. Anterior
 - b. Posterior
 - c. Anterior-Septal
 - d. Anterior-Lateral
 - e. Lateral
 - f. Inferior-lateral
4. QRS duration

Other secondary endpoints collected will be:

1. 6 month complete loss of capture threshold as defined in the primary endpoint.
2. 12 month complete loss of capture threshold as defined in the primary endpoint

Methods

Design

Single center, open label, randomized pilot study to evaluate the complete ventricular capture thresholds of His Bundle versus left bundle area pacing.

Secondary analysis will focus on echocardiographic hemodynamic parameters of HIS pacing, versus left bundle branch pacing.

Based on previous studies ([Vijayaraman, Naperkowski, et al., 2018](#)) and our experience with non-selective and left bundle area pacing, a difference of 0.5 V at 1.0 ms in capture threshold at 3 month follow-up between His and left bundle area pacing sites, is to be expected. With a standard deviation of 0.5 V, This would require an enrollment of 20 patients to obtain a power of 0.8 to demonstrate

statistical significance. Thus we anticipate enrollment of 26 patients to evaluate differences in capture threshold between the studied pacing sites, and an expected 20% patient drop out.

Enrollment

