Investigators providing care will be tasked with patient screening. This will be performed at both the inpatient and outpatient arenas, and can occur within any timeframe prior to the pacemaker implant. During the screening process, patients will be given consent forms to be reviewed collectively with an investigator.

Statistical Analysis

Continuous variables will be reported as mean +/- standard deviation. Categorical variables will be expressed as percentages. Paired comparisons will be made using a Student t-test if the data is normally distributed, and with the Wilcoxon signed-rank test for nonparametric data. Paired categorical data will be compared using the Wilcoxon test. P-value ≤ 0.05 was considered significant.

Randomization

Randomization will be in a 1:1 assignment. Twenty-six envelopes with random assignments to one of the two treatment arms will be created. As patients are enrolled, they will be assigned to an envelope. Each envelope number will be correlated with patient information, as well as date of procedure, and assigned ID number.

Randomization will occur after the patient demonstrates acceptable selective or non-selective HIS bundle pacing prior to active fixation.

If the patient is identified at the Beaumont Troy site, the above shall still continue to apply. The key personnel will bring the randomization card to the site on the day of the procedure.

Study Population

Inclusion Criteria

Prospective enrollment of patients:

1. Over 18 years old
2. Signed consent
3. Pacemaker indication according to 2018 ACC/ AHA HRS Guideline on the Evaluation and Management of Patients with Bradycardia and Cardiac Conduction Delay with one or more of the following
 - a. Symptomatic sinus node dysfunction.
 - b. Symptomatic Atrioventricular (AV) block or high degree AV block.
 - c. Tachy-Brady syndrome

Exclusion Criteria

Patients with any condition of the following will be excluded:

1. Previously implanted cardiac pacing devices except transvenous temporary pacemaker.
2. Patients who are eligible for appropriate cardiac resynchronization therapy(CRT) or implantable cardiovert defibrillator (ICD) implantation
3. Patients with prior septal myectomy
4. Patients with prior surgical or transcatheter aortic valve replacement
5. Anatomy precluding implant evaluated during the screening or identified during the procedure.

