The lead and sheath will be withdrawn to the tricuspid valve annulus. A unipolar intracardiac electrogram will be recorded from the lead tip using electrophysiological recording system in order to identify a selective His bundle electrogram. Once a discrete His bundle electrogram is identified, unipolar pacing, at a pulse duration of 1.0 ms, will be initiated to elicit selective or non-selective HIS Bundle pacing based on criteria outlined by prior authors ([Vijayaraman, Chung, et al., 2018](#)). Effort will be made to achieve selective His bundle pacing, but if non-selective His bundle pacing can be elicited, this is acceptable.

Once selective or non-selective His bundle capture is demonstrated, the patient is randomized to His or left bundle area pacing for active fixation.

If the patient does not have the anatomy suitable for identifiable selective or non-selective HIS bundle capture, they will be removed from the study. Instead, they will undergo active fixation of the lead to the RV apex, septum, or left bundle area. This will be at the discretion of the operator.

If the patient is randomized, active fixation of the lead will be performed based on randomization to either His bundle or left bundle area pacing site.

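### The plan names only paired tests, so the primary comparison between two independent randomised arms has no applicable test, and the stated power of 0.8 does not hold for a two-sample test

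*Combined protocol and SAP*

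**What the plan says.** The primary objective is between sites: "To compare 3 month follow up complete ventricular capture thresholds of His bundle pacing versus left bundle area pacing lead placement". Under Randomization the ratio is 1:1, and "Twenty-six envelopes with random assignments to one of the two treatment arms will be created". Under Procedural Protocol, once His capture has been shown, "the patient is randomized to His or left bundle area pacing for active fixation". The ventricular lead is then fixed at the allocated site only.

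The Statistical Analysis section is the only place where tests are named. After the descriptive summaries it gives two sentences on testing: "Paired comparisons will be made using a Student t-test if the data is normally distributed, and with the Wilcoxon signed-rank test for nonparametric data", and "Paired categorical data will be compared using the Wilcoxon test". It sets the significance level at 0.05 without saying one- or two-sided.

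Other comparisons also run between arms. The Secondary Objectives open with "To compare changes in left ventricular performance and mechanical synchrony" and add later thresholds, such as "6 month complete loss of capture threshold as defined in the primary endpoint". Potential Risks says adverse outcomes will be compared between the two cohorts.

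The sample-size paragraph under Design assumes a 0.5 V difference and an SD of 0.5 V. It states that 20 patients give power 0.8, and plans 26 to allow for 20% dropout. It shows no formula and does not say what the SD refers to.

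**The concern.** Each patient contributes one 3-month threshold from one site, so the primary comparison contains no pairs. A paired t-test or signed-rank test cannot be applied to it without inventing pairs. The named tests do suit repeats within a patient, such as acute against follow-up threshold or baseline against 3-month echo. The defect is therefore an omitted between-arm test.

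Three things are at stake:

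- **Primary analysis.** It needs a choice that the plan does not make, so the test could be chosen after the data are seen.
- **Changes.** If the named paired tests are run in each arm and the two p-values contrasted, a difference between arms may be claimed when the true change is the same in both.
- **Power.** If the stated power of 0.8 is not met by a two-sample test, readers who believe it will over-interpret a non-significant result.

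**Working it through.** **1. Tests against comparisons**

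| Comparison in the plan | Data structure | Named test that fits |
|---|---|---|
| 3-month threshold (primary) | two independent groups | none |
| 6- and 12-month thresholds | two independent groups | none |
| Change in echo measures and QRS duration, His v left bundle area | two independent groups of changes | none |
| Adverse outcomes between cohorts | two independent groups, yes/no | none |
| Repeats within a patient | paired | Student t-test or signed-rank |

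**2. The plan's figure of 20**

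Inputs from Design: difference 0.5 V, SD 0.5 V, power 0.8. The level of 0.05 is from Statistical Analysis. Assumptions: 0.5 V is the per-patient SD, and the test is two-sided. The standardised difference is d = 0.5/0.5 = 1.0.

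- Two-sample, two-sided: 16 per arm (32 in all) by normal approximation; 17 per arm (34) by exact t.
- Two-sample, one-sided: 13 per arm (26) or 14 per arm (28).
- Reading 20 as the number per arm: power 0.87, and it conflicts with 26 enrolled in total.
- Paired t with an SD of differences of 0.5 V: 10 pairs, power 0.803.

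No two-sample version gives 20. Ten pairs are 20 measurements, which would fit a paired calculation, but with no formula shown this remains a conjecture. The dropout step is consistent: 20/(1 − 0.2) = 25, or 26 for equal arms.

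**3. Power of a two-sample t-test at the planned size**

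Power comes from the noncentral t with n1 + n2 − 2 degrees of freedom and noncentrality d/√(1/n1 + 1/n2). The 95% CI half-width is t(0.975) × 0.5 × √(1/n1 + 1/n2). Dropout of 20% from 26 is 5.2 patients, leaving about 21.

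| Evaluable | Noncentrality | Power, two-sided | Power, one-sided | 95% CI half-width |
|---|---|---|---|---|
| 20 (10 v 10) | 2.236 | 0.562 | 0.694 | 0.470 V |
| 21 (11 v 10) | 2.289 | 0.584 | 0.713 | 0.457 V |
| 26 (13 v 13) | 2.550 | 0.687 | 0.797 | 0.405 V |

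For example, at 10 v 10 the half-width is 2.101 × 0.5 × √0.2 = 0.470 V.

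Two-sided power 0.8 at 10 v 10 needs d = 1.325: a difference of 1.325 × 0.5 = 0.66 V, or an SD of 0.5/1.325 = 0.377 V. With other SDs at 10 v 10, power is 0.75 (SD 0.4 V) and 0.42 (SD 0.6 V). By simulation with normal data, rank-sum power is about 0.51 at 10 v 10 and 0.64 at 13 v 13.

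**4. Cost of choosing the test afterwards**

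In 40,000 simulated normal trials at 10 v 10 with no true difference, rejection rates were 0.050 for Welch, 0.044 for rank-sum and 0.057 for either one significant.

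**5. Separate paired tests in each arm (illustration)**

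Take 10 patients per arm and the same true change in both. If p is the power of one paired test, the chance that exactly one arm is significant is 2p(1 − p).

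| True change (in SDs of change) | p | 2p(1 − p) |
|---|---|---|
| 0 | 0.050 | 0.095 |
| 0.5 | 0.293 | 0.414 |
| 0.7 | 0.506 | 0.500 |
| 1.0 | 0.803 | 0.316 |

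**The case against.** The best defence is that the section is loosely drafted and that paired was meant as pairwise, His against left bundle area. The text says Student t-test without qualification, and on that reading a two-sample t-test would be covered. But its stated non-parametric partner is the signed-rank test, which needs one-sample or paired data. Even the generous reading leaves no valid fallback for non-normal thresholds and no test for the yes/no adverse outcomes.

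A second argument is that the harm to the primary endpoint is small. A paired test has no pairs to run on, so an analyst would probably use an independent t-test or rank-sum test, and choosing between them afterwards raises the type I error only to about 5.7%. That is right. The arm-by-arm figures describe a misuse that the plan does not prescribe; they show where the named tests could lead, not what will happen.

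Third, the power figures depend on what the SD means and on sidedness, neither of which is stated. That also stands, so the figures are conditional. It does not restore the claim: one-sided power with 20 patients is 0.69, and two-sided power reaches 0.8 only if the per-patient SD is about 0.38 V.

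That the trial is a pilot does not excuse the gap, because the plan itself claims power for statistical significance.

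**Conclusion.** The concern holds and should be fixed before the data are analysed. No test in the plan applies to the primary comparison or to any other between-arm comparison. This follows from the text and needs no numerical assumption.

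The stated power of 0.8 with 20 patients does not hold for a two-sample test. Power is about 0.56 to 0.58 at the expected evaluable number, assuming a two-sided 0.05 test and 0.5 V as the per-patient SD. The consequence for type I error on the primary endpoint is slight. The weightier consequences are an overstated power and the risk of contrasting within-arm p-values for the change endpoints.

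**What to change.** In Statistical Analysis:

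1. Name in advance one independent-samples test for the 3-month threshold, for example Welch's t-test with mean difference and 95% CI. Name the Wilcoxon rank-sum test as its non-parametric counterpart, say which of the two is primary, and state sidedness. Use the same test at 6 and 12 months.
2. Compare changes in LVEF, stroke volume, QRS duration and, where a baseline exists, tissue Doppler timing directly between arms. Use ANCOVA on baseline or a two-sample test of change, chosen beforehand.
3. Use Fisher's exact test for yes/no outcomes, including adverse outcomes.
4. Keep the paired tests for within-arm description only.

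In the sample-size paragraph under Design, say what the 0.5 V SD refers to. If it is the per-patient SD, restate two-sided power as about 0.56 with 20 evaluable, 0.58 with 21 and 0.69 with 26. Keep 26 enrolled and present the pilot as estimating the difference, with a 95% CI of about ±0.47 V at 10 per arm.

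This costs wording only: no new patients, envelopes, visits or data. The price is a less favourable stated power. If the sponsor prefers to keep 0.8, exact t on the same assumptions needs 34 evaluable patients, and 34/0.8 = 42.5, so 43 enrolled (44 for equal arms); that would no longer be a wording change.

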6. Those without ability to achieve selective His bundle pacing evaluated during the screening or identified during the procedure
7. Pregnant women

Pre-Operative Characterization

After enrollment, patients will be evaluated in the Heart Rhythm Center Holding Center, prior to pacemaker implant.

A baseline 12 lead EKG will be obtained prior to or at the onset of the procedure, and the following will be collected.

1. QRS duration
2. QRS morphology

Patients will then be randomized, after the selective or non-selective HIS bundle pacing can be achieved, to either selective His bundle, or left bundle pacing site for active fixation of the ventricular lead.

The following baseline characteristics will be collected:

1. Age
2. Sex

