If the left bundle area location is selected, the sheath and lead tip will be advanced to the anterior lower site of His bundle position, and then rotated in a counterclockwise fashion to place the lead tip in a perpendicular orientation to the IVS. To signify the site of left bundle area pacing, the following parameters should be sought; (1)A typical “W” with a notch at the nadir of the QRS complex in lead V1, or qR paced morphology in surface lead V1, (2) A shorter pacing-to-QRS interval than the initial His-bundle pacing-to-QRS interval, (3) and no His potential identified during intrinsic rhythm. Unipolar pacing will be performed at a pulse duration of 1.0 ms, and an output which allows for the narrowest complex QRS. The lead will then be screwed into the IVS by performing 4-5 initial clockwise revolutions of the fixation screw. To avoid penetration into the left ventricular cavity, intermittent observation of the impedance values, and anatomic septal penetrance by surface echo evaluation will be performed. An additional 4-5 clockwise revolutions will be performed, until impedance values start to drop, and the fixation screw has penetrated to the left septum on surface echo. Published expected impedance values and depth of penetrance have recently been published to be used as a template ([Vijayaraman P & Mascarenhas V, 2019](#)

) Afterwards, a small (<5 mL) contrast injection will be delivered through the sheath to verify septal penetration of the lead. Left bundle capture will be accepted if there is narrowing of the QRS when compared to pre-fixation QRS width at the proposed left bundle area site, or narrowing if the QRS complex at higher outputs indicating conduction system capture. A RBBB is expected, but not required for capture of the left bundle branch.

If the selective His site is to be used for active fixation, the lead will be placed with at least 5 revolutions of the screw into the myocardium.

The atrial lead will be inserted and actively fixed.

Device

The leads will be connected to Medtronic dual chamber pacemaker generator. The device will be placed in the pocket and the pocket will be closed with sutures in a standard manner as per the operator.

Echocardiographic Evaluation Protocol

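### Exclusions 5 and 6 stay open through a procedure in which randomisation happens midway, and no analysis population is defined, so arm-specific removal after allocation is not ruled out

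*Combined protocol and SAP*

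**What the plan says.** **Timing of randomisation.** The Randomization section states: "Randomization will occur after the patient demonstrates acceptable selective or non-selective HIS bundle pacing prior to active fixation". Procedural Protocol agrees: "Once selective or non-selective His bundle capture is demonstrated, the patient is randomized to His or left bundle area pacing for active fixation". Pre-Operative Characterization gives the same order.

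**Exclusions.** Exclusion Criteria item 5 is "Anatomy precluding implant evaluated during the screening or identified during the procedure". Item 6 is "Those without ability to achieve selective His bundle pacing evaluated during the screening or identified during the procedure". Neither says that it ceases to apply once the patient is allocated.

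**Removal during the procedure.** Procedural Protocol describes one case, placed before allocation: "If the patient does not have the anatomy suitable for identifiable selective or non-selective HIS bundle capture, they will be removed from the study". It then says that randomised patients have the lead fixed according to their allocation.

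**Left bundle arm.** Positioning at the septum, screwing in and the acceptance check follow allocation. The check begins "Left bundle capture will be accepted if there is narrowing of the QRS when compared to pre-fixation QRS width", and narrowing at higher outputs is an alternative. No text says what happens to a randomised patient who meets neither.

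**Envelopes.** The Randomization section also says "As patients are enrolled, they will be assigned to an envelope". That may be before the procedure, and so before any intra-procedural exclusion.

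**Analysis.** Statistical Analysis names tests and a significance level. It defines no analysis population and no intention-to-treat rule. It does not say how failed fixation, a lead at the other site or exclusion after randomisation is handled. The Design section makes the trial open label.

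**The concern.** Every patient shows His capture before allocation. Whether a left bundle lead can be placed is first tested after allocation, and only in patients assigned to it. An exclusion that remains available for the whole procedure can then be invoked by someone who knows the arm, for a reason that arises mainly in that arm. If such patients leave the analysis, the groups compared are no longer the randomised groups. With 13 patients per arm, one removal is 1/13 = 7.7% of an arm.

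Item 6 adds a separate difficulty. It excludes patients in whom selective His pacing cannot be achieved, while three other sections allow randomisation on non-selective capture. A validly randomised patient can therefore still meet an exclusion criterion.

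**Working it through.** **1. Order of events.**

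| Step | Before or after allocation | Arms | What the plan says about removal |
|---|---|---|---|
| Access, sheath passage, mapping at the annulus | Before | All | Item 5 may apply |
| Test of selective or non-selective His capture | Before | All | Removed if neither is obtained |
| Allocation | – | – | – |
| Septal positioning, screwing, acceptance check | After | Left bundle only | Item 5 has no cut-off; no rule if not accepted |
| Fixation at the His site | After | His only | Items 5 and 6 have no cut-off |

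Only failure of His capture is tied to the period before allocation. The other intra-procedural exclusions have no time limit.

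**2. The plan's own figures.** Inputs from the Design section are a difference of 0.5 V, SD 0.5 V, power 0.8, 20 patients, 20% drop-out and 26 enrolled. The drop-out step is consistent: 20/(1 − 0.2) = 25, or 26 as an even number. The 20 is not reproduced for two parallel groups. A two-sided two-sample t-test at 0.05 (sidedness is my assumption) needs 17 per arm, or 34. A one-sided test needs 14 per arm, or 28. That is a separate matter, and this point does not depend on it. It does set the scale: 26 split 1:1 is 13 per arm, with two-sided t-test power of 0.69. Losing 1, 2 or 3 patients from one arm lowers power to 0.67, 0.65 or 0.62 before any bias.

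**3. Possible bias, by assumption.** The documents give no exclusion rate and no link between the reason for exclusion and threshold. I assume normal thresholds with SD 0.5 V, no true difference, 13 per arm, and *k* patients dropped from one arm only.

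If exactly the *k* highest are dropped, the shift is SD × (sum of the *k* largest expected normal order statistics) / (13 − *k*). For 13 observations the three largest expected values are 1.668, 1.164 and 0.850.

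- *k* = 1: 0.5 × 1.668/12 = 0.07 V
- *k* = 2: 0.5 × 2.832/11 = 0.13 V
- *k* = 3: 0.5 × 3.682/10 = 0.18 V

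If patients are dropped on a difficulty score that correlates ρ with threshold, the shift is ρ times these values. Simulation (100,000 trials per case, two-sided t-test) agrees and adds the type I error:

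| Dropped of 13 | Shift, ρ = 0.3 | Shift, ρ = 0.5 | Shift, highest dropped | Type I error, ρ = 0.3 to 0.5 | Type I error, highest dropped |
|---|---|---|---|---|---|
| 1 | 0.020 V | 0.034 V | 0.069 V | 0.052–0.054 | 0.073 |
| 2 | 0.039 V | 0.065 V | 0.129 V | 0.054–0.064 | 0.111 |
| 3 | 0.057 V | 0.092 V | 0.185 V | 0.058–0.073 | 0.164 |

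Against the 0.5 V target, the moderate case is 0.020/0.5 = 4% to 0.092/0.5 = 18%. The extreme case is 0.069/0.5 = 14% to 0.185/0.5 = 37%. With symmetric thresholds, dropping the lowest values instead gives the same sizes with the opposite sign.

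**The case against.** The other side has several fair points.

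- **Item 5 speaks of anatomy that precludes implant, not of anatomy that precludes the allocated site.** A septum that will not take a left bundle lead need not preclude implant, since His capture has already been shown. The phrase about the procedure also has a natural meaning before allocation. This stands as a possible reading, but the text does not settle it. The only response the plan gives to a technical failure during the procedure is removal, so a reader could extend that to a failed left bundle attempt.
- **Allocation is to be respected.** Procedural Protocol fixes the lead by allocation, so it would be wrong to say that the plan is silent on treatment after randomisation. Potential Risks also compares exit block, threshold increase, dislodgement and lead revision between cohorts, which suggests that later failures are kept. Neither covers failure at the first fixation, and neither is an analysis rule.
- **Losing selective capture at fixation is not plainly covered by item 6.** That stands. For item 6 the firm point is the conflict between selective and non-selective capture.
- **A reader might infer that the worst thresholds would be removed and the left bundle arm flattered.** The documents do not support this. The primary endpoint is complete loss of ventricular capture, and non-selective pacing includes local myocardium, so failing to reach the left bundle does not imply a high threshold. Acceptance rests on QRS narrowing, and narrowing at higher outputs also counts.
- **The 20% drop-out allowance might be thought to cover this.** It replaces lost numbers. It does not correct selective loss from one arm.

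**Conclusion.** The concern holds as an ambiguity in the exclusion rules combined with a missing analysis rule. As written, item 5 can be read to permit removal after randomisation by people who know the arm. The left bundle arm is the likeliest place, because feasibility there is first tested after allocation. Item 6 conflicts with the randomisation criterion.

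The documents permit such removal; they do not show that it happened or would happen. Direction and size are unknown. For 1 to 3 of 13 dropped from one arm, the illustration gives about 0.02 to 0.09 V with type I error about 0.05 to 0.07 if the reason correlates 0.3 to 0.5 with threshold. The upper bound is about 0.07 to 0.19 V with type I error about 0.07 to 0.16. All of this rests on assumed counts, normality, the plan's SD of 0.5 V and the assumed correlation.

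**What to change.** 1. Add to exclusions 5 and 6: *applied only until the randomisation envelope is opened*. State in Randomization that the envelope is opened only once eligibility is confirmed.
2. Add to Statistical Analysis: *All randomised patients are followed and analysed in the arm to which they were allocated, whatever the final lead site; an analysis by final lead site is supportive; intra-procedural exclusions are reported by timing and arm.* This is workable because complete loss of ventricular capture can be measured wherever the ventricular lead ends up.
3. Reconcile item 6 with Randomization, Pre-Operative Characterization and Procedural Protocol on selective versus non-selective capture. Which criterion applies is for the investigators to decide.

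None of this adds a lead-placement rule. The operator discretion in Procedural Protocol concerns only patients removed before randomisation, and should not be read as covering randomised patients.

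The cost is a few sentences, with no added patients or visits. Some allocated patients may end with a lead at another site, which dilutes the contrast by an amount the documents do not allow one to estimate, in a trial whose two-sided power is only 0.69 with 13 per arm.
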